3.1.2. Secondary

To determine the accuracy with which viability imaging predicts global functional recovery

To explore the relationship between viability, revascularisation, functional recovery, and clinical outcome.

4. Data available

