4.1. Sample size

In REVIVED-BCIS2 all patients underwent viability imaging prior to randomisation; at least four viable segments which could be revascularised by PCI were required for inclusion. Of the 700 patients enrolled, viability was assessed with CMR in 491 and DSE in 187. Primary outcome data are available for 99.1% of patients. Serial echocardiographic data are available for a subset of these patients.

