6.2. Secondary outcomes

While several secondary clinical outcomes were specified in the main trial protocol, for the Viability Study SAP, these will be restricted to all-cause death, cardiovascular death and heart failure hospitalisation, each analysed in the same manner as the primary composite outcome. Improvement of left ventricular function at six months is the key secondary outcome and will be defined in a binary manner, as an improvement in LV ejection fraction greater than the median change in LVEF at six months.

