7.2. Viability and improvement in left ventricular ejection fraction

A Cox proportional hazards model will be used to assess the relationship between the number of viable myocardial segments (treated as a linear effect) and recovery of left ventricular function at six and twelve months. Multivariable Cox analyses will be used to adjust the analysis for the list of baseline factors in section 7.1. The interaction between viability and treatment assignment on improvement in left ventricular function will then be assessed using a Cox proportional hazards model containing the following co-variates: viability (treated as a linear effect), randomly assigned treatment, and their interaction, plus the aforementioned list of baseline risk factors. In secondary analyses, the extent of viability will be divided into tertiles and Kaplan-Meier curves stratified by both viability tertile and treatment assignment presented. A sensitivity analysis will be performed where viability is defined irrespective of resting dysfunction (including segments with normal function at rest and with $\leq 25\%$ scar on CMR or contractile reserve on DSE).

The relationship between the number of viable segments and recovery of left ventricular function will also be assessed using the change in ejection fraction at 6 and 12 months with a linear mixed effects model for repeated measures adjusting for the variables specified in section 7.1⁷. This model accounts for the baseline ejection fraction, while also incorporating both follow-up measurements, and enables the inclusion of participants with missing measurements. The mean change in ejection fraction at each timepoint along with the association between viability and these means will be estimated. The model includes a variable for time, viability, and an interaction between time and viability, and assumes no effect of treatment at baseline. An unstructured variance-covariance matrix will be used to allow for correlations between repeated measures of ejection fraction. The model will be fitted using restricted maximum likelihood and assumes that missing ejection fraction values are missing-at-random.

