9.2. Wall motion score index prediction of LV recovery and mortality

The wall motion score index (WMSI) is a unitless number that is proportional to the severity and extent of wall motion abnormalities on stress echocardiography calculated by dividing the sum of the individual segment scores by the total number of segments scored. A WMSI >2.19 has been shown to be predictive of mortality or poor functional result in patients undergoing surgical revascularisation however this has yet to be tested in patient undergoing percutaneous coronary revascularisation. ROC curves will be constructed to identify a cut-off WMSI predicting poor outcomes in those undergoing percutaneous revascularisation.

9.3. Relationship between the number of viable segments on DSE and improvement in LV function following revascularisation

Using the AHA 16 segment model for analysis of regional wall motion score will allow the relationship between the total number of viable segments and global improvement in LV function to be explored; additionally segmental recovery will also be assessed using paired student's T test.

9.4. Comparison of sustained improvement in wall motion vs biphasic response of segments in predicting LV recovery

A biphasic response to dobutamine ("low vs high dose") has been found to be a more sensitive predictor of myocardial viability as compared with sustained improvement, moreover the biphasic response was found to be a predictor of global improvement in LV function after surgical revascularisation¹⁸. A comparison of sustained improvement vs biphasic response utilising Cox regression analysis will be carried out to identify if a biphasic response is a more sensitive predictor of myocardial recovery following percutaneous coronary revascularisation.

10. References

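### Viability SAP 9.4 asks which stress-echo response is the more sensitive predictor of recovery, but its only method, Cox regression, does not estimate or compare sensitivity

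*Protocol*

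**What the plan says.** Section 9.4 sits in Appendix 2 of the Viability Study SAP (DSE secondary analyses). It cites earlier work in which the biphasic response "has been found to be a more sensitive predictor of myocardial viability as compared with sustained improvement", then sets the analysis: a comparison of sustained improvement with biphasic response "utilising Cox regression analysis will be carried out to identify if a biphasic response is a more sensitive predictor of myocardial recovery" after PCI. No other method is named there.

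Other parts of the same SAP bear on the point:

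- Section 3.1.2 lists as a secondary objective: "To determine the accuracy with which viability imaging predicts global functional recovery".
- Section 6.2 defines recovery as a binary outcome, "an improvement in LV ejection fraction greater than the median change in LVEF at six months". Section 7.2 works with "recovery of left ventricular function at six and twelve months".
- Section 8.4 (CMR) uses ROC curves, Youden's index and DeLong's comparison. Section 9.2 (DSE) uses ROC curves to find a wall motion score cut-off.
- Section 9.1 repeats the main viability analysis in DSE patients. For recovery, that analysis (section 7.2) consists of Cox and mixed models.
- Section 4.1 gives the numbers: "viability was assessed with CMR in 491 and DSE in 187".

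**The concern.** The question in 9.4 concerns the probability of a response given recovery. The method concerns the rate of recovery given a response. These are linked through the frequency of each response in patients or segments that do not recover, so an answer to one is not an answer to the other. Replacing Cox with logistic regression would not help, because it conditions in the same direction. The point is therefore separate from whether Cox is suitable for an outcome read at fixed visits.

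At stake is one sentence in a sub-study report. A significant hazard ratio could be written up as showing that the biphasic response is the more sensitive, or a null one as showing equal sensitivity, and neither would follow from the analysis. No other section fills the gap: ROC methods are assigned to CMR scar in 8.4 and to the wall motion score in 9.2, but not to this comparison.

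**Working it through.** **No figure to reproduce.** Section 9.4 gives no sample size, power or error rate. The check is whether the Cox contrast tracks sensitivity.

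**Inputs from the documents.** There were 187 DSE patients. Half of them (187/2 = 93.5, taken as 93) approximates the PCI arm, which is the group the question concerns. Recovery means an LVEF change above the median, so prevalence is about 50%. Visits are at 6 and 12 months.

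**Inputs assumed.** The documents do not give the response frequencies in recovered (s) and non-recovered (f) patients. A two-sided 5% test is assumed, with one mutually exclusive response category per patient: biphasic, sustained or neither.

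**Step 1: what each quantity conditions on.** Sensitivity = P(pattern | recovered) = s. By Bayes' rule with prevalence 0.5,

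P(recovered | pattern) = 0.5s / (0.5s + 0.5f) = s / (s + f).

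The Cox contrast follows the second quantity, which moves with f even when s is fixed.

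**Step 2: equal sensitivities, 40% v 40%, 93 patients.**

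| Non-recoverers: biphasic v sustained | Predictive value, biphasic | Predictive value, sustained | Cox rejection |
|---|---|---|---|
| 10% v 50% | 0.40/0.50 = 0.80 | 0.40/0.90 = 0.44 | up to about 81% |
| 20% v 40% | 0.40/0.60 = 0.67 | 0.40/0.80 = 0.50 | from about 5% |
| 10% v 20% | 0.40/0.50 = 0.80 | 0.40/0.60 = 0.67 | about 1% to 16% |
| 15% v 20% | 0.40/0.55 = 0.73 | 0.40/0.60 = 0.67 | about 0% to 6% |

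The first two rows together span about 5% to 81%. The spread within a row comes from Breslow or Efron handling of ties and from one or two event times. Because recovery is read only at visits, nearly all event times are tied, so this choice matters. A direct test of the two sensitivities among recoverers rejects about 3% to 4% of the time in the first two rows.

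**Step 3: unequal sensitivities, 60% v 20%, equal predictive values.** Taking non-recoverers at 30% v 10% as an example, 0.60/0.90 = 0.20/0.30 = 0.67. Cox rejection stays below the nominal 5%. The direct test has about 86% power.

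**Step 4: a second set, with all 187 DSE patients and two visits.** The assumption is that 70% of recoveries are seen at 6 months.

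- Sensitivities 35% v 35%, non-recoverers 10% v 35%: hazard ratio 2.03 (Efron) or 1.71 (Breslow).
- Control, equal sensitivities and equal non-recoverer rates: hazard ratio about 1.0, rejection 1% to 4%.
- Sensitivities 50% v 25% with equal predictive values of 0.71: hazard ratio about 1.0, rejection 1% to 5%.

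The Cox contrast departs from 1 when predictive values differ and not otherwise, whatever the sensitivities are. Note that 187 counts both arms and is an upper bound for a post-PCI analysis.

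**The case against.** Four things can fairly be said for the plan.

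1. **Wording.** The heading of 9.4 speaks only of predicting LV recovery, and 'more sensitive' may be loose for 'stronger', which an association model does address. This is possible. But sensitivity is a defined term in diagnostic imaging and 8.4 uses it in that sense. On either reading, the aim or the method has to change.

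2. **The larger rejection rates come from chosen extremes.** In the first two rows of the table the sustained response is uninformative or inverse (likelihood ratio 40/40 = 1.0 or 40/50 = 0.8), while the biphasic response has a ratio of 40/20 = 2 or 40/10 = 4. The biphasic response really is the better predictor there, and rejection is an error only as a statement about sensitivity. With both patterns informative, Cox rejection was about 0% to 16%. This stands. A reader might infer that the planned analysis would usually produce a false claim; the documents do not support that, since they give no response frequencies.

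3. **Unit.** The heading refers to the response of segments, and a patient may have mixed responses. The calculation uses one response per patient. This stands as a limit on the figures, not on the logic.

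4. **Sensitivity alone is a poor yardstick.** For mutually exclusive patterns, a difference in sensitivity partly reflects how common each pattern is. In Step 3 the biphasic response is three times as common in recoverers and in non-recoverers, so neither pattern discriminates better, yet a test of sensitivity alone would favour biphasic. This stands and shapes the fix.

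**Conclusion.** The mismatch is real: 9.4 poses a question about sensitivity and names only a method that does not measure it. This follows from the definitions and rests on no assumed number. Its practical size is unknown. The range of about 0% to 81% for Cox rejection under equal sensitivities depends on assumed response rates, on 93 patients with one response each, and on tie handling. It shows that the error can occur, not how likely it is here.

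Two stronger readings are not supported. One is that the Cox analysis is uninformative: it can still describe association with recovery. The other is that the trial's findings are at risk: this is an exploratory analysis in a DSE-only appendix, with no error rate or decision rule attached, and neither the primary endpoint nor the main viability analyses in sections 7.1 to 7.3 depend on it. It is a minor point, worth correcting because the correction is cheap.

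**What to change.** In section 9.4, state the unit of analysis (patient or segment) and which of the SAP's recovery definitions applies. Then, in PCI patients:

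- estimate sensitivity and specificity of each response pattern for recovery, with 95% confidence intervals, clustering by patient if the analysis is by segment;
- compare the patterns with paired (McNemar-type) tests among recoverers and among non-recoverers, and interpret the two results jointly, not on sensitivity alone;
- show predictive values or likelihood ratios alongside.

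If the regression is kept, restate its aim as association between response pattern and recovery, and draw no conclusion about sensitivity from it.

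The cost is a wording change and a little extra analysis on data already planned. There is one drawback: with mutually exclusive patterns, a sensitivity difference partly reflects how common each pattern is, and the report should say so.
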